6.2.6 Missing Last Dates of Study Drug Dosing

If the date of last dose of study drug is completely missing, then the date of last dose of study drug will be taken for analysis purposes as the date when the subject would have run out of study drug assuming full compliance from the date the study drug was last dispensed, or the date of subject's last clinic visit in the study (if study drug is returned) or early withdrawal or death whichever the earlier.

If only the month and year of the last dose was recorded, then the date of last dosing will be taken for analysis purposes as the date the subject would have run out of study drug assuming full compliance from the date the study drug was last dispensed, the last day of the month of the recorded last dose or the date of subject's last clinic visit in the study (if study drug is returned) or early withdrawal or death whichever the earlier.

6.2.7 Prior Analgesic Use

Subjects will be classified as those who have previously taken gabapentin, pregabalin or duloxetine versus those who have not taken any of these, based on prior medications reported.

6.2.8 Exposure to Study Drug

Exposure to study drug (days) will be calculated as follows:

(Date of last dose of study drug - Date of first dose of study drug) + 1

The exposure calculation will not take into account breaks in therapy.

6.2.9 Treatment Compliance

Treatment compliance will be calculated per visit interval (Visit 2 to Visit 4, Visit 4 to Visit 5, and Visit 5 to Visit 6) as follows:

$\frac{Total\ number\ of\ capsules\ dispensed-Total\ number\ of\ capsules\ returned}{(Number\ of\ days\ within\ the\ visit\ interval)}\times 100$

Total number of capsules dispensed will be obtained as below:

- Visit 2 to Visit 4: the total number of capsules dispensed at Visit 2
- Visit 4 to Visit 5: the total number of capsules dispensed at Visit 4
- Visit 5 to Visit 6: the total number of capsules dispensed at Visit 5

Total number of capsules returned will be obtained as below:

- Visit 2 to Visit 4: the total number of capsules returned at Visit 4
- Visit 4 to Visit 5: the total number of capsules returned at Visit 5
- Visit 5 to Visit 6: the total number of capsules returned at Visit 6

The number of days within the visit interval is obtained as follows:

- Visit 2 to Visit 4: (Date of Visit 4 Date of first dose of study drug) + 1
- Visit 4 to Visit 5: (Date of Visit 5 Date of Visit 4)
- Visit 5 to Visit 6: (Date of Visit 6 Date of Visit 5)

The number and percentage of subjects with compliance \geq 80% will also be provided by treatment group for each interval.

6.2.10 Inexact Values

In the case where a laboratory parameter has result recorded as "> x", " \geq x", " \leq x" or " \leq x", a value of x will be taken for analysis purposes.

6.2.11 Electrocardiogram Data

For electrocardiogram (ECG) data recorded on continuous scales, if more than one value (for instance, triplicate recordings) is recorded at a time point (i.e., date), the mean value rounded to the integer will be presented. in the event that one reading is missing, the average of the available two readings will be used for the analysis. Furthermore, if only one reading is available, this reading will be used for the analysis.

For overall interpretation if more than one interpretation is recorded, the most severe (worst case) interpretation will be presented.

6.2.12 Early Withdrawal Assessments

For the analysis, assessments performed at early withdrawal visits for the subjects who discontinued will be mapped to the closest visit, using midpoints between visits to window the early withdrawal. If the early withdrawal assessment is mapped to a visit where a scheduled assessment is already present, the scheduled assessment will take precedence, and the early withdrawal assessment will be disregarded (and listed only).

Note that the windowing will be specific to the measure, per the below table. For example, PGI-C is collected at Weeks 4, 8, and 12 and thus the early withdrawal assessment for PGI-C would be windowed with Day 2 to Day 42 as Week 4, Day 43 to Day 70 as Week 8, and Day 71+ as Week 12. The BPI-DPN is collected at Weeks 4 and 12. Thus, early withdrawal assessments would be windowed with Day 2 to Day 56 as Week 4, and Day 56+ as Week 12.

Assessment(s)	Timing of Early Withdrawal Assessment	Mapped Visit
PCS, Physical Exam	Day 2+	Week 12
BPI-DPN,	Day 2 to Day 56	Week 4
Norfolk QoL-DN	Day 57+	Week 12
ECG	Day 2 to Day 70	Week 8
ECG	Day 71+	Week 12
Vital signs, Laboratory	Day 2 to Day 42	Week 4
samples,	Day 43 to Day 70	Week 8
PGI-C	Day 71+	Week 12
	Day 2 to Day 21	Week 2
Sheehan STS	Day 22 to Day 42	Week 4
Sheehan 515	Day 43 to Day 70	Week 8
	Day 71+	Week 12

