# 11. STOPPING CRITERIA

Subjects will be withdrawn from the treatment period of the study if any of the following laboratory results and symptoms are observed.

- ALT or AST >8xULN Discontinue subject treatment immediately.
- ALT or AST >5xULN

ALT or AST >3xULN and (TBL >2xULN or INR >1.5)

Discontinue treatment if result is confirmed upon retest (to be done within 48 hours or as soon as feasible).

- ALT or AST >3xULN with the appearance of fatigue, nausea, vomiting, right upper quadrant pain or tenderness, fever, rash, and/or eosinophilia (>5%)
- ALT or AST >3xULN that persists for  $\geq$  4 weeks

If an increase of serum aminotransferase of >3xULN is identified, repeat testing within 48 to 72 hours of all four of the usual serum measures (ALT, AST, ALP, and TBL) should conducted to confirm the abnormalities and to determine if they are increasing or decreasing.

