6.2.13 Unscheduled Visits

Unscheduled visits will be handled in an identical manner as described in Section 6.2.12. If this results in multiple records for a given visit, then the scheduled visit will take highest precedence, followed by early withdrawal visits, and unscheduled visits last.

6.2.14Change from Baseline

Change from baseline in absolute terms is defined as the baseline value subtracted from the postbaseline values. This calculation method will be used as part of the calculation for percentage change from baseline calculations.

Change from Baseline = Post-baseline Value - Baseline Value

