6.12.2 Laboratory Data

Descriptive statistics for the observed values and change from baseline will be presented by treatment group and visit for each hematology, urinalysis, and serum chemistry (including triglycerides and thyroid panel) parameter. Each continuous measurement will be classified as below, within, or above normal range, based on ranges supplied by the laboratory used. Categorical parameters may also be classified as normal or abnormal based on normal ranges, and subject counts within each category will be summarized. Shift tables in relation to the normal range from baseline to each post-baseline visit will be presented.

Summaries and listings will be presented using the original unit for each parameter as received from the analytical laboratory.

A listing of out of normal range laboratory values throughout the study will be presented. All laboratory assessments, including urine pregnancy tests, drug tests, and serology will also be listed.

A separate listing will be provided for all Alanine Aminotransferase (ALT), Aspartate Aminotransferase (AST), and Bilirubin results at all timepoints for any subjects who meet the criteria for liver function abnormalities as defined in Section 6.2.25.

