6.12.6 Sheehan-Suicidality Tracking Scale

Descriptive statistics for observed and change from baseline S-STS total score will be summarized by treatment group for each post-baseline visit.

All S-STS responses throughout the study will be listed.

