16.2.6.2	Average Pain Intensity Upon Walking in the Past 24 Hours, Weekly Mean NRS Score - Modified Intent-to-Treat Population	IP	16.2.6.1

16.2.6.4 Daily Rescue Medication (Acetaminophen 500 mg) Usage - Modified Intent-to-Treat Population IP 16.2.6.5 Daily Sleep Interference Scale - Modified Intent-to-Treat Population IP 16.2.6.6 Pain Catastrophizing Scale - Modified Intent-to-Treat Population IP 16.2.6.7 Brief Pain Inventory for Diabetic Peripheral Neuropathy - Modified Intent-to-Treat Population IP 16.2.6.8 Norfolk Quality of Life Questionnaire - Diabetic Neuropathy - Modified Intent-to-Treat Population IP 16.2.6.9 Patient Global Impression of Severity - Modified Intent-to-Treat Population IP 16.2.6.10 Patient Global Impression of Change - Modified Intent-to-Treat Population IP 16.2.6.11 Sheehan-Suicidality Tracking Scale - Modified Intent-to-Treat Population IP 16.2.6.12 Average Pain Intensity Related to DPN, Time to First ≥30% or ≥50% Reduction (Days) in Mean NRS Score - Modified Intent-to-Treat Population IP 16.2.7 Adverse Event Listings IP 16.2.7.1 Adverse Event Data - Safety Population IP	16.2.6.3	Worst Pain Intensity Related to DPN in the Past 24 Hours, Weekly Mean NRS Score - Modified Intent-to-Treat Population	IP	16.2.6.1
16.2.6.5 Daily Sleep Interference Scale - Modified Intent-to-Treat Population 16.2.6.6 Pain Catastrophizing Scale - Modified Intent-to-Treat Population IP	16.2.6.4	Daily Rescue Medication (Acetaminophen 500 mg) Usage -	IP	

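### Early-termination and unscheduled labs, vital signs, ECGs and S-STS that share a window with a scheduled value are listed but not tabulated, and no worst-post-baseline summary by arm picks them up

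*SAP*

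**What the plan says.** SAP 6.2.12 has early-withdrawal assessments "mapped to the closest visit, using midpoints between visits to window the early withdrawal". For labs, vital signs and PGI-C they are "windowed with Day 2 to Day 42 as Week 4, Day 43 to Day 70 as Week 8, and Day 71+ as Week 12". ECG has two windows (Day 2 to 70 is Week 8, Day 71 onward is Week 12). The S-STS has an extra Week 2 window (Day 2 to 21, then Day 22 to 42 for Week 4). Where a scheduled value already occupies the mapped visit, "the scheduled assessment will take precedence, and the early withdrawal assessment will be disregarded (and listed only"). SAP 6.2.13 treats unscheduled visits in the same way, and with several records in one window "the scheduled visit will take highest precedence, followed by early withdrawal visits, and unscheduled visits last".

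The safety tables are built on those visits. For labs, SAP 6.12.2 adds to the descriptive statistics: "Shift tables in relation to the normal range from baseline to each post-baseline visit will be presented". Vital signs (6.12.3), ECG (6.12.5) and S-STS total score (6.12.6) are also summarized visit by visit. The table list in SAP Section 11 contains no worst-post-baseline, any-time or last-value table for any of them.

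The fallback is listings. SAP 6.12.2 to 6.12.6 list all labs, out-of-range labs, vital signs, ECGs and S-STS responses. Output 14.3.4.1 shows ALT, AST and bilirubin at every time point for subjects who exceed three times ULN on ALT or AST, or twice ULN on bilirubin (SAP 6.2.25, 6.12.2). On the S-STS, SAP 6.12.6 says "All S-STS responses throughout the study will be listed", but the list of outputs has "16.2.6.11 Sheehan-Suicidality Tracking Scale - Modified Intent-to-Treat Population".

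**The concern.** One mapping rule serves efficacy and safety data alike. For a by-visit efficacy estimate, preferring the scheduled record is sensible. For safety, the record taken when a subject stops, or at an extra visit called because something looked wrong, is often the informative one, and it is the one that gives way. Protocol 6.1 provides unscheduled visits for safety concerns and abnormal laboratory or ECG findings, and these records rank last.

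Safety and tolerability form part of the primary objective, and the S-STS is a named safety endpoint (Protocol 5.1, 5.3.3). Protocol Section 4 describes tolerability for up to four weeks of dosing. With visits on nominal days, every displaced lab and vital-sign day falls after Day 28, where by-arm data on this drug are new. The same section reports aminotransferase rises in earlier studies. If abnormal values at stopping were more common on one arm, the by-visit tables would understate the difference in measured values.

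**Working it through.** **Reproducing the plan's cut-offs.** Nominal visit days are 14, 28, 56 and 84 (Protocol Table 3). Midpoints: (14+28)/2 = 21; (28+56)/2 = 42; (56+84)/2 = 70; and for measures taken only at Weeks 4 and 12, (28+84)/2 = 56. All agree with the table in SAP 6.2.12.

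**When an early-termination value is displaced.** This happens when the stop falls after the scheduled visit in its window and on or before that window's last day. Possible stop days are Day 2 to Day 83, which is 82 days. With visits on nominal days:

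- Labs and vital signs: Days 29–42 (14) and 57–70 (14), so 28/82 = 34%.
- S-STS: the same 28 days plus Days 15–21 (7), so 35/82 = 43%.
- ECG: Days 57–70 (14), so 14/82 = 17%.

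On all other days no scheduled value is yet in the window, so the early-termination value is tabulated.

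**Sensitivity to visit timing.** Protocol Table 3 allows ±2 days at Week 2 and ±4 days at Weeks 4 and 8. With all visits at the early edge (Days 12, 24, 52), the displaced days are 36 for labs and vital signs, 45 for S-STS and 18 for ECG. At the late edge (Days 16, 32, 60) they are 20, 25 and 10.

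**Subjects.** SAP Section 4 plans 204 randomized with 15% drop-out: 0.15 × 204 = 30.6. The assumptions are stops spread evenly over Days 2–83, every earlier scheduled visit attended, and an early-termination visit held.

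| Measure | Share of days (range) | Subjects, both arms (range) |
|---|---|---|
| Labs, vital signs | 34% (24–44%) | 30.6 × 28/82 = 10.4 (7.5–13.4) |
| S-STS | 43% (30–55%) | 30.6 × 35/82 = 13.1 (9.3–16.8) |
| ECG | 17% (12–22%) | 30.6 × 14/82 = 5.2 (3.7–6.7) |

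**Unscheduled values.** They rank last, so in a subject who attends every scheduled visit they do not enter the by-visit tables.

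**Liver retests.** Protocol Section 11 asks, once an aminotransferase exceeds three times ULN, for "repeat testing within 48 to 72 hours of all four of the usual serum measures (ALT, AST, ALP, and TBL". A retest two or three days after an in-window visit falls on Days 26–35 (Week 4), 54–63 (Week 8) or 82–91 (Week 12). Each range lies inside that visit's own window, so the retest always yields to the scheduled value that prompted it. That scheduled value stays in the tables. The trigger is also the entry criterion for output 14.3.4.1, so each such subject's ALT, AST and bilirubin appear there, retest included. The retested ALP does not.

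**Example.** A subject has normal ALT on Day 28 and stops on Day 35 for an unrelated reason, with ALT raised but not above three times ULN. The Day 35 value maps to Week 4 and is displaced. It does not enter the liver listing, and under Protocol 9.4.1 it need not be an adverse event. It appears only in the lab listings. Had the subject stopped on Day 45, the value would have been tabulated as Week 8.

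**The case against.** A reader might infer that results from subjects who stop because of harm, and mandated liver retests, disappear from the report. The documents do not support that, for four reasons.

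- **Listings.** Displaced values are listed, as the rule itself says.
- **Liver retests.** Every subject with a mandated retest meets the criterion for the Section 14 liver listing, and the triggering value stays tabulated.
- **Adverse event tables.** These are by arm and do not use the mapping. Qualifying lab abnormalities that lead to interruption or discontinuation must be recorded as adverse events (Protocol 9.4.1), as must post-baseline suicidality (9.3.6) and clinically significant ECG changes (9.3.4, 12.7.3). Events leading to discontinuation have their own table.
- **Share of days kept.** On nominal days the early-termination value is kept on 66% of stop days for labs and vital signs and on 83% for ECG, so the exclusion is partial.

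It can also be said that labs, vital signs and ECG are not named safety endpoints, that the protocol promises only mean change for labs and vital signs, and that all safety summaries are descriptive.

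Much of this stands, and it limits the point to by-arm summaries of measured values. Within that limit it does not close the gap. A listing is not a comparison by arm. The liver listing is confined to three analytes above set thresholds. Protocol 9.4.1 keeps many lab abnormalities out of the adverse event data, ECG entry rests on the investigator's judgement, and event counts do not show the size of a change. The S-STS is a named endpoint whose only planned table is a by-visit total score.

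Two further points are fair. The mITT restriction on the S-STS listing will rarely matter: a dosed subject with no diary entry has most likely left before Week 2, and an early-termination S-STS would then be tabulated in the Safety Population. For ECG, SAP 6.2.11 presents the worst interpretation when several are recorded, without saying whether this applies across dates mapped to one visit. Exclusion from the ECG interpretation shift table is therefore unclear rather than established.

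**Conclusion.** The point holds as a gap in the by-arm summary of measured safety values, not in safety reporting as a whole. Displaced early-termination and unscheduled labs, vital signs, ECG measurements and S-STS scores are listed but enter no table.

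On nominal visit days this touches about a third of possible stop days for labs and vital signs, more for S-STS and fewer for ECG: at most about 10, 13 and 5 subjects over both arms. These counts use all-cause drop-out. Missed scheduled visits, or drop-outs with no final visit, would lower them. Early attendance would raise them to about 13, 17 and 7, and uneven timing of drop-out could move them either way. How many would have stopped because of harm cannot be derived from the documents, so a claim that the tables hide a known share of harm-related values goes too far.

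The change is still worth making: it affects what the by-arm tables show on a co-primary safety objective, and it needs no new data.

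**What to change.** 1. Keep the precedence rule for the by-visit rows. Removing it for safety data would leave no rule for choosing one record per visit.
2. Add by-arm worst-post-baseline summaries for labs, vital signs, ECG and S-STS total score: shift from baseline to worst value, in each relevant direction, using all scheduled, early-termination and unscheduled records in the Safety Population.
3. State in SAP 6.2.11 how the worst-case ECG interpretation rule works with the precedence rule when records from different dates map to the same visit.
4. Change Listing 16.2.6.11 to the Safety Population so that it agrees with SAP 6.12.6.

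The cost is a few sentences of SAP text, some added table rows and one listing population. The downside is slightly longer tables.

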6.2.13 Unscheduled Visits

Unscheduled visits will be handled in an identical manner as described in Section 6.2.12. If this results in multiple records for a given visit, then the scheduled visit will take highest precedence, followed by early withdrawal visits, and unscheduled visits last.

6.2.14Change from Baseline

Change from baseline in absolute terms is defined as the baseline value subtracted from the postbaseline values. This calculation method will be used as part of the calculation for percentage change from baseline calculations.

Change from Baseline = Post-baseline Value - Baseline Value

6.2.15 Percent Change from Baseline

Percent change from baseline will be calculated as change from baseline multiplied by 100 then divided by the baseline value.

Percent Change from Baseline =
$$\frac{\textit{Change from Baseline} \times 100}{\textit{Baseline Value}}$$

6.2.16 Pooled Sites

The study protocol indicates that study site will be included as factor in statistical models. It was further indicated that the study can include up to 37 study sites in the United States. It is likely that some of these sites will have small numbers of subjects included in the mITT population, which could lead to convergence issues, unreliable treatment effect estimates and p-values. Thus, in the event that there are study sites with fewer than 6 subjects included in the mITT population, these sites will be pooled together to form a single site, such that the pooled sites will have a minimum of 6 subjects included in the mITT. The resulting pooled sites (referred to as "site" from here on) will be used in the analyses.

6.2.17 Numerical Rating Scale

The Numerical Rating Scale (NRS) is a unidimensional, segmented numeric scale in which a respondent selects a whole number (0-10 integers) that best reflects the intensity of the pain. The

format is a horizontal bar or line that is anchored by terms describing pain levels where a score of 0 represents "no pain" and a score of 10 represents "worst pain imaginable". Subjects will report pain intensity during the past 24 hours daily at bedtime in the handheld diary.

NRS score will be obtained for:

- Average pain intensity related to DPN in the past 24 hours
- Average pain intensity upon walking in the past 24 hours
- Worst pain intensity related to DPN in the past 24 hours

6.2.17.1 Baseline Mean NRS Score

The baseline mean NRS score is defined as the average of the NRS scores on the last 7 days prior to the first dose of study drug (Study days -7 to -1). A minimum of 5 non-missing NRS scores out of the 7 days is required for the baseline mean NRS score.

Baseline NRS = Sum of daily NRS scores (over 7 days)/ Number of available diaries

6.2.17.2 Post-Baseline Weekly Mean NRS Scores

Weekly Mean NRS Scores for Week 12 (and prior weeks) will be obtained based on the subject's actual Week 12 visit date. If the subject's Week 12 visit date is within Day 80 to Day 88, then the 7th NRS score for Week 12 will be the corresponding NRS score on the day before the subject's Week 12 visit date, and the 6th to 1st NRS score for Week 12 will be obtained backwards from this. Thus, the corresponding NRS scores on the last 7 days prior to Week 12 actual visit date will be used for Week 12. Consequently, the Week 11 NRS scores will be obtained by counting 7 days backwards from the 1st NRS score for Week 12, Week 10 NRS scores will be obtained by counting 7 days backwards from the 1st NRS score for Week 11 and continuing up to Week 1. If the subject's actual Week 12 visit date is beyond Day 88, then the corresponding NRS score on the day before Day 88 (i.e., Day 87) will be used as the 7th NRS score for Week 12, and the 6th to 1st NRS score will be obtained backwards from this and continuing for each week from Week 11 to Week 1. Meanwhile, if the subject's actual Week 12 visit date is earlier than Day 80, then no Week 12 data will be identified.

Timing of Week 12 Visit	Reference Day (NRS)
Day 80 to Day 88	Count backwards from day before Week 12 visit
Day 80 to Day 88	(Week 12 study day -1)

Day 89+	Count backwards from Day 87 only	
Earlier than Day 80	No Week 12 data identified	

For subjects that withdraw early or have missing data such that they do not have any data that would fall into the Week 12 windowing, their last non-missing diary day will serve as the anchor; weeks will be counted backwards in 7-day intervals from the last day. For the week ending with this anchor day, study week will be assigned such that the majority of days fall in the nominal week. For example, Week 11 is nominally day 71-77; if a subject's last value is on day 74, the majority of the resulting 7-day window working backwards would be in "Week 11", so their last week would be analyzed as "Week 11" and the subsequent intervals assigned descending weeks working backwards. The following table shows how the last interval will be assigned based on its last day.

Timing of Last Non-Missing Diary	Assigned Week
	(from which to count backwards)
Day 1 to Day 10	Week 1
Day 11 to Day 17	Week 2
Day 18 to Day 24	Week 3
Day 25 to Day 31	Week 4
Day 32 to Day 38	Week 5
Day 39 to Day 45	Week 6
Day 46 to Day 52	Week 7
Day 53 to Day 59	Week 8
Day 60 to Day 66	Week 9
Day 67 to Day 73	Week 10
Day 74 to Day 80	Week 11
NA	Week 12

Change from baseline and percent change from baseline will be calculated by subtracting baseline mean score from the post-baseline weekly mean scores, as defined in Sections 6.2.14 and 6.2.15.

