### 9.2.4. Daily Sleep Interference Scale

The DSIS was developed to quantify sleep interference due to pain. The DSIS is a single -item measure that is completed by patients once a day (upon awakening) to accurately capture variability in sleep interference due to pain on a daily basis, thus minimizing recall bias. The DSIS has an 11-point response scale that asks patients to "Select the number that best describes how much your pain has interfered with your sleep during the past 24 hours." Response options range from 0 (did not interfere with sleep) to 10 (completely interfered with sleep/unable to sleep due to pain). The DSIS is designed to be used in a patient daily diary that patients fill out upon awakening each morning [Vernon 2008].

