3.2 Secondary Endpoints

The secondary efficacy endpoints are:

- Change from baseline in the weekly mean of the Daily Sleep Interference Scale (DSIS) scores at Week 12.
- Percentage of subjects 'much improved' or 'very much improved' on Patient Global Impression of Change (PGI-C) at Week 12.
- Percentage of subjects achieving ≥30% pain reduction from baseline in the weekly mean NRS average pain intensity related to DPN at Week 12.
- Percentage of subjects achieving ≥50% reduction from baseline in the weekly mean NRS average pain intensity related to DPN at Week 12.
- Change from baseline to Week 12 in Norfolk Quality of Life Questionnaire Diabetic Neuropathy (QOL-DN) score.
- Use of rescue medication, including the proportion of subjects using rescue medication, the frequency and amount used.
- Cumulative response (percent reduction from baseline) in the weekly mean NRS average pain intensity at Week 12.
- Change from baseline in the weekly mean Numerical Rating Scale (NRS) score assessing average pain intensity related to DPN at each week from Week 1 through Week 12.

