6.2.3 Duration / Study Day / Time

Study day will be calculated as the number of days from first dose of study drug.

- date of event date of first dose of study drug + 1, for events on or after first dose
- date of event date of first dose of study drug, for events before first dose

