If the subject's Week 12 visit date is within Day 80 to Day 88, then data on the actual Week 12 visit date up to 6 days prior to this date will be the corresponding data for Week 12 visit date. Consequently, the Week 11 data will be obtained by counting 7 days backwards from the 1st day of Week 12, Week 10 NRS scores will be obtained by counting 7 days backwards from the 1st day of Week 11, and the process continue up to Week 1. If the subject's actual Week 12 visit date is beyond Day 88, then the corresponding data from Day 82 to Day 88, inclusive, will be the Week 12 data. Similar process as described previously will be used to obtain the data for each week from Week 11 up to Week 1. Meanwhile, if the subject's actual Week 12 visit date is earlier than Day 80, then no Week 12 data will be identified.

Timing of Week 12 Visit	Reference Day (DSIS or Rescue Medication)
Day 80 to Day 88	Count backwards from day of Week 12 visit
Day 89+	Count backwards from Day 88 only
Earlier than Day 80	No Week 12 data identified

For subjects that withdraw early or have missing data such that they do not have any data that would fall into the Week 12 windowing, their last non-missing diary day will serve as the anchor, as described in Section 6.2.17.2.

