6.11.1.2 Primary Efficacy Analysis

A restricted maximum likelihood (REML)-based mixed model for repeated measures (MMRM) will be utilized to analyze the change from baseline to Week 12 in the weekly mean of the NRS score assessing average pain intensity related to DPN in the past 24 hours.

The MMRM model will have site, treatment group, week, baseline NRS score, and treatment-by-week interaction as terms in the model. The unstructured covariance (UN) will be utilized as the within-subject covariance structure in the event that the model fails to converge using the UN, the covariance structure among Toeplitz (TOEP), first-order autoregressive [AR(1)], and compound symmetry (CS) for which the model converges and yields the least corrected Akaike's information criterion (AICC) will be used. The Kenward-Roger degrees of freedom correction will also be used for this analysis.

The estimate of the treatment difference at Week 12 and standard error (SE) will be derived from this model. Observed NRS scores at baseline and at each week, as well as their change from baseline at each week will be presented by treatment group. The LS means, corresponding SEs, and 95% CI for each treatment group, as well as the estimate, corresponding SE, and p-value of the treatment difference in LS means at each week will be presented.

The following is the sample SAS code that will be used for this analysis:

```
PROC MIXED DATA= DATAIN;

CLASS USUBJID TREATMENT WEEK SITE;

MODEL CFB = TREATMENT WEEK SITE TREATMENT*WEEK BASELINE / DDFM=KR;

REPEATED WEEK / SUBJECT=USUBJID TYPE=UN;

LSMEANS TREATMENT*WEEK / CL DIFF;

RUN;
```

A line plot showing the LS means and 95% CIs of the weekly mean NRS scores from Week 1 through Week 12 for each treatment group will be presented.

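### NRS Week 1 has no floor at Day 1, so baseline diaries enter it when the Week 12 visit falls on Day 80 to 84

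*SAP*

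**What the plan says.** **Weekly NRS means (SAP 6.2.17.2).** For a Week 12 visit on Day 80 to 88, the last Week 12 score is the one from the day before the visit. Weeks 11 to 1 follow in 7-day steps, with Week 10 and earlier obtained by "counting 7 days backwards from the 1st NRS score for Week 11 and continuing up to Week 1". A visit after Day 88 is anchored on Day 87. Early withdrawals, and subjects with no diary in the Week 12 window, are anchored on their last diary day. A table assigns that day to a week. The worked example is a subject whose "last value is on day 74, the majority of the resulting 7-day window working backwards" falls in Week 11.

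**Baseline (SAP 6.2.17.1).** The baseline mean uses the scores "on the last 7 days prior to the first dose of study drug (Study days -7 to -1").

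**Study days (SAP 6.2.3).** A study day is the event date less the "date of first dose of study drug + 1, for events on or after first dose". Events before the first dose do not get the added 1, so Day -1 is followed directly by Day 1.

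**Visit window (Protocol Table 3).** The Week 12 visit is due on Day 84 ± 4.

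**Where Week 1 is used.** SAP 3.2 lists as a secondary endpoint the change in weekly mean NRS for "average pain intensity related to DPN at each week from Week 1 through Week 12". Under SAP 6.11.1.2 the estimate, SE and "p-value of the treatment difference in LS means at each week will be presented". Weeks 1 to 12 also supply the MMRM, the line plot and the imputation model in 6.11.1.3.1.

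**Sleep scale (DSIS, SAP 6.2.18).** The back-count is the same, but Week 12 takes "data on the actual Week 12 visit date up to 6 days prior to this date".

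**The concern.** A weekly change from baseline should set post-dose scores against pre-dose scores. The back-count fixes the end of Week 12 and lets the start of Week 1 fall where it may. If the visit is on target or early, Week 1 starts before the first dose, and every pre-dose day it takes in already belongs to the baseline window. The same diaries then stand on both sides of the subtraction, and part of the Week 1 change is zero on average by construction.

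At stake are the first point of the weekly secondary endpoint with its p-value, the first point of the line plot, and the Week 1 input to the MMRM and the imputation model. The SAP plans independent programming of derived data (6.3.3). Without a written rule, two programmers could reasonably derive different Week 1 values.

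**Working it through.** **1. The plan's own table.** Nominal Week 11 is Days 71 to 77. A last diary on Day 74 gives the window Day 68 to 74, with four days (71 to 74) in nominal Week 11 and three in Week 10, so Week 11 is assigned, as the SAP says. Applying the majority rule to each last-diary day from 1 to 80, with days before Day 1 left out of the vote, reproduces the SAP's table with no mismatch.

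**2. NRS with a Week 12 visit on Day V (80 to 88).** Twelve adjacent blocks need 12 × 7 = 84 days. From Day 1 to Day V − 1 there are V − 1 days. The shortfall is 84 − (V − 1) = 85 − V when positive. With no Day 0, it is filled from Day -1 backwards.

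| Visit day | Week 1 covers | Baseline diaries, k | Post-dose diaries, 7 − k | Shrinkage k/7 |
|---|---|---|---|---|
| 80 | Day -5 to 2 | 5 | 2 | 71% |
| 81 | Day -4 to 3 | 4 | 3 | 57% |
| 82 | Day -3 to 4 | 3 | 4 | 43% |
| 83 | Day -2 to 5 | 2 | 5 | 29% |
| 84 | Day -1 to 6 | 1 | 6 | 14% |
| 85 | Day 1 to 7 | 0 | 7 | 0 |
| 86 to 88 | starts Day 2, 3, 4 | 0 | 7 | 0 |

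The last column assumes complete diaries, pre-dose diaries in Week 1 that average the subject's baseline mean B, and post-dose scores at a constant B + c. The Week 1 change is then [k × 0 + (7 − k) × c]/7 = c(7 − k)/7.

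**3. Early-withdrawal anchor.** A last diary on Day L assigned to Week w needs 7w days and has L, so the shortfall is 7w − L when positive.
- Week 1 row (Days 1 to 10): positive for L = 1 to 6, which is 6 days.
- Each of the ten rows for Weeks 2 to 11 runs from L = 7w − 3 to 7w + 3: positive for the first three days, which is 3 × 10 = 30.
- Total: 6 + 30 = 36 of 80 table days. These are days in the table, not a share of subjects.
- The SAP's Day 74 example: 77 − 74 = 3, so Week 1 is Day -3 to Day 4.

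**4. Week 12.** The block is Day V − 7 to V − 1. The earliest case, V = 80, is Day 73 to 79, so it holds no pre-dose days.

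**5. Sleep scale.** Anchored on the visit day, the shortfall is 84 − V: 4, 3, 2 and 1 baseline-window days for visits on Day 80 to 83, and none from Day 84. The Protocol describes the scale thus: "The DSIS is designed to be used in a patient daily diary that patients fill out upon awakening each morning". The first dose is taken in the clinic, so the Day 1 entry is also expected to precede dosing.

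**6. Group level.** Neither the spread of visit days nor the onset of effect is given. For illustration only, with a flat effect and visits spread evenly over the stated days:
- Days 84 to 88: (1/7)/5 = 2.9%
- Days 83 to 85: (3/7)/3 = 14.3%
- Days 80 to 88: (15/7)/9 = 23.8%

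If the effect builds over time, the result also depends on how far each subject's weeks are shifted, which is a different matter from the missing floor. No figure is given for that case.

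**7. Rescue medication (separate point).** The reference-day table in 6.2.18 anchors it on the visit day, while 6.2.19 refers to the NRS method, which ends the day before. Use is recorded at bedtime, and Protocol Table 3, footnote b, ends diary completion the night before the Week 12 visit. On the visit-day anchor, Week 12 then has at most 6 of 7 entries for visits on Day 80 to 88. A raw weekly sum is 1 − 6/7 = 14% low under constant daily use.

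**The case against.** **The wording already implies a post-dose start.** The section heading and the change definition in 6.2.14 speak of post-baseline values, the assignment table begins at Day 1, and the moving average in 6.2.17.4 starts at Day 1. A reader might infer either that the floor is in force or that the plan means to reuse baseline diaries. Neither is supported. The wording suggests what was intended, but no rule in 6.2.17.2 sets a floor, and the back-count as written crosses Day 1. This is a gap in the derivation.

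**The count could be inclusive.** If each block shared a day with the next, Week 1 would start on Day 7 to 11 for visits on Day 80 to 84 and hold no baseline diaries. But the weeks would overlap and the first post-dose days would be dropped, and the same section later speaks of 7-day intervals. Adjacent blocks are the natural reading.

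**The NRS Day 1 entry also looks back over pre-dose hours.** True, but it is recorded at bedtime after dosing and lies outside the baseline window, so it is not used twice.

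**The reach is small.** This stands. The rule is the same in both arms. Week 1 is one of twelve points, and the SAP makes no multiplicity adjustment for secondary endpoints (Section 9, item 10). For the sleep scale, 6.11.2.1 plans a p-value at Week 12 only, so its Week 1 is descriptive and a model input. A reader might infer that the primary Week 12 comparison is contaminated. Its block holds no pre-dose diaries, and any indirect effect through the model has not been quantified. Nor do the documents support a claim of bias for or against the drug, or of any particular group-level loss.

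**Conclusion.** The point holds for Week 1. As written, and with complete diaries, the rule puts 5, 4, 3, 2 and 1 baseline diaries into NRS Week 1 for visits on Day 80 to 84. Those are five of the nine days in the visit window, including the target day. The counts are exact given adjacent blocks and no Day 0; missing diaries would lower them. The 14% to 71% shrinkage is for a single subject and rests on the flat-effect assumption. The upper end needs a visit at the early edge of the window, while an on-target visit brings in one diary of seven.

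The consequence is a distorted first point of a named secondary endpoint and a poorly defined model input, which is worth correcting because it is cheap. The rescue-medication conflict is real, and on the visit-day anchor it reaches a Week 12 total. It is a separate minor point and adds no weight to this one.

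**What to change.** - **SAP 6.2.17.2:** state that post-baseline weekly NRS means use only diaries from study Day 1 onward, with the back-count otherwise unchanged. Limit any minimum-diary rule for truncated windows to Week 1, so that Week 12 is not affected.
- **SAP 6.2.18:** state an equivalent post-dose floor for the sleep scale as a study day. Day 2 is the first morning entry expected to follow dosing.
- **SAP 6.2.18 and 6.2.19 (separate):** reconcile the two rescue-medication reference days, checking the choice against footnote b of Protocol Table 3. If Week 1 is cut to post-dose days, express it as mean daily use or prorate it to 7 days, because a raw total over fewer days would be low for that reason alone.

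**Cost.** A few sentences and one programming condition per measure. NRS Week 1 would rest on 2, 3, 4, 5 and 6 diaries for visits on Day 80 to 84. If the baseline minimum of 5 diaries were carried over, Week 1 would be missing for visits on Day 80 to 82, so that choice should be made openly. The floor does not align weeks between subjects: NRS Week 1 still ends on Day 2 for a Day 80 visit (80 − 78) and on Day 10 for a Day 88 visit (88 − 78).
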